8.11.3.2 Contrast Volume per Stratification Group (1, 2, 3 or more vessel PCI)

The total undiluted iodinated contrast volume (in ml) used per PCI (from first positioning the interventional guiding catheter in stable coronary position till end of PCI procedure) in each stratification group, i.e., 1 vessel PCI, 2 vessel PCI and 3 or more vessel PCI.

Descriptive summaries of the total undiluted iodinated contrast volume will be presented by treatment group and by stratification group (1 vessel PCI, 2 vessel PCI and 3 or more vessel PCI) for the FAP and the PP population and will include the number of subjects with non-missing data (n), mean with 95% confidence interval, standard deviation (SD), median, interquartile range (IQR) and minimum and maximum values.

The endpoint will be evaluated per subgroup (1 vessel PCI, 2 vessel PCI and 3 or more vessel PCI) using a one-sided two-sample t-test. We will test for assumptions, e.g. normality and equal variances. Normality will be checked using histograms and Q-Q plots. If there are strong indications of non-normality, the data will be (log)transformed, and the back transformed results will be presented. Levene's test for equality of variances will be applied. When the p-value of this test is greater than 0.05, then we assume the variances are equal and we will use the arithmetic mean of the variances in calculating the standard error. When the p-value is less than or equal to 0.05, then we assume the variances are unequal and then we will calculate the standard error from the weighted average of the two variances.

The results of the t-test will be displayed as estimates of the between treatment group difference (with 95% confidence intervals) and the (one-sided) p-value for the between treatment group difference. When the p-value is lower than the significance level of 2.5% (alpha) we will reject the null hypothesis.

All subjects in the FAP population will be included in this analysis. The analysis will be repeated for the PP population.

Document ID:	<As applicable, per local requirements>	Document title:		Classification:	For internal use
		Statistical Analysis Plan			
Modified:	11MAY2023			Author:	
Version:	3.0	Template ID:	ClinicalStudyTemplate0025	Approver:	
Status:	Final	Template Version Date:	02MAR2018	Page:	32 of 52

Statistical Analysis Plan

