8.1.1 Sample Size Justification Primary Endpoint

A recent single center, non-randomized, retrospective study [Yabe 2018] has shown to achieve 21.9% contrast reduction when using Dynamic Coronary Roadmap compared to the control group without using Dynamic Coronary Roadmap, see Table 2.

	Control group	DCR group
Number of patients	103	43
Iodinated contrast volume (ml) average \pm standard deviation	152.1 ± 73.0	118.8 ± 49.7

Table 2 Results of a recent pilot study [Yabe 2018]

To determine the sample size for the primary endpoint of this study we used the Yabe study outcomes as input with a margin of 7% for the contrast reduction, i.e., the sample size calculation is performed to reliably show a 15% contrast reduction in the DCR group compared to the control group not using Dynamic Coronary Roadmap.

For the sample size and power calculations we have set:

- Estimated mean for the Control group = 152.1 (based on [Yabe 2018])
- Estimated mean for the DCR group = 129.3 (15% reduction)
- Estimated standard deviation = 73.0 (based on [Yabe 2018])
- Effect size (standardized difference): $(152.1 - 129.3)/73.0 = 0.3123$
- Significance: one-sided $\alpha = 0.025$ (the type I error, i.e., probability of rejecting a true null hypothesis)

Document ID:	<As applicable, per local requirements>	Document title:		Classification:	For internal use
		Statistical Analysis Plan			
Modified:	11MAY2023			Author:	
Version:	3.0	Template ID:	ClinicalStudyTemplate0025	Approver:	
Status:	Final	Template Version Date:	02MAR2018	Page:	21 of 52

Statistical Analysis Plan

- Power (1- β) = 80%

Sample sizes of 162 for each group achieves 80% power to reject the null hypothesis of equal means when the population mean difference is 15% with a standard deviation of 73.0 for both groups and with a significance level (alpha) of 0.025 using a one-sided two-sample equal-variance t-test (calculated by PASS 16.0.3 software).

Finally the percentage of subjects that are expected to be lost at random during the course of the study (drop-out rate) and for whom no response data will be collected (i.e., will be treated as "missing") needs to be taken into account. A drop-out rate of 10% (DR=0.1) is assumed, meaning that $162/(1-DR)=180$ patients are needed in each group totaling 360 patients for the primary endpoint.

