8.1.2 Sample Size Justification Secondary Endpoint

A recent single center, non-randomized, prospective study [Rajappan 2017] showed a 25.6% reduction in the median number of cine X-ray runs after introduction of Dynamic Coronary Roadmap, see Table 3.

	Enrollment group 1	Enrollment group 4
Number of patients	21	21
Number of cine X-ray runs	Average: 46.2 SD: 22.4 Median: 43.0 IQR: 31-54	Average: 34.6 SD: 21.2 Median: 32.0 IQR: 20-43
Number of stents	Average: 1.76 SD: 0.89	Average: 1.67 SD: 0.86

Table 3 Results of a recent pilot study [Rajappan 2017]

For the sample size and power calculations we have set based on [Rajappan 2017]:

- Estimated mean for the Control group = 46.2
- Estimated mean for the DCR group = 34.6

Document ID:	<As applicable, per local requirements>	Document title:	Classification:	For internal use
Modified:	11MAY2023	Statistical Analysis Plan		
Version:	3.0	Template ID:	ClinicalStudyTemplate0025	Approver:
Status:	Final	Template Version Date:	02MAR2018	Page: 22 of 52

Statistical Analysis Plan

- Estimated median for the Control group = 43.0
- Estimated median for the DCR group = 32.0
- Significance: one-sided $\alpha = 0.025$ (the type I error, i.e., probability of rejecting a true null hypothesis)
- Power $(1-\beta) = 80\%$

Sample sizes of 177 for each group achieves 80% power to reject the null hypothesis of equal population distributions with a significance level (alpha) of 0.025 using a one-sided Wilcoxon-Mann-Whitney test, since the number of angiographic X-ray runs is discrete and is likely to be not normally distributed (calculated by SAS software).

This means for the secondary endpoint on Number of Angiograms that $177/(1-DR)=197$ patients are needed in each group, so 394 in total which is higher than the total number of patients (360) required for the primary endpoint, so **a total of 394 subjects are required for this study.**

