8.11.3.3 Contrast Volume per Simple, Intermediate, Complex PCI subgroup

The total undiluted iodinated contrast volume (in ml) used per PCI (from first positioning the interventional guiding catheter in stable coronary position till end of PCI procedure) in subgroups of simple, intermediate and complex PCI.

Descriptive summaries of the total undiluted iodinated contrast volume will be presented by treatment group and by complexity in tertiles for the FAP and the PP population and will include the number of subjects with non-missing data (n), mean with 95% confidence interval, standard deviation (SD), median, interquartile range (IQR) and minimum and maximum values.

The endpoint will be evaluated per subgroup using a one-sided two-sample t-test. We will test for assumptions, e.g. normality and equal variances. Normality will be checked using histograms and Q-Q plots. If there are strong indications of non-normality, the data will be (log)transformed, and the back transformed results will be presented. Levene's test for equality of variances will be applied. When the p-value of this test is greater than 0.05, then we assume the variances are equal and we will use the arithmetic mean of the variances in calculating the standard error. When the p-value is less than or equal to 0.05, then we assume the variances are unequal and then we will calculate the standard error from the weighted average of the two variances.

The results of the t-test will be displayed as estimates of the between treatment group difference (with 95% confidence intervals) and the (one-sided) p-value for the between treatment group difference. When the p-value is lower than the significance level of 2.5% (alpha) we will reject the null hypothesis.

All subjects in the FAP population will be included in this analysis. The analysis will be repeated for the PP population.

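### The vessel-number and SYNTAX-tertile analyses give a separate reject verdict in each level and never assess whether the effect differs between levels; at the planned effect, an identical effect would give mixed verdicts about 71% of the time across tertiles

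*SAP*

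**What the plan says.** Two exploratory sections of the SAP compare contrast volume between arms within subgroups. SAP 8.11.3.2 covers number of vessels: "The endpoint will be evaluated per subgroup (1 vessel PCI, 2 vessel PCI and 3 or more vessel PCI) using a one-sided two-sample t-test". SAP 8.11.3.3 covers complexity, defined in SAP section 6 as tertiles of the patient's overall SYNTAX score: "The endpoint will be evaluated per subgroup using a one-sided two-sample t-test". In both sections the null hypothesis is rejected in a level when its one-sided p-value is below 2.5%. That makes six verdicts in the full analysis population, and the six tests are repeated in the per-protocol population. SAP 8.15 makes no multiplicity adjustment.

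Both sections also report the between-group difference with a 95% confidence interval in each level.

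No other section adds a comparison between levels. SAP 8.13 only says that the primary endpoint will be analysed by these factors. SAP 8.14 describes ANCOVA and random-center models with treatment and covariates as fixed effects and no treatment-by-covariate term. Protocol 7.8.2 and 7.8.3 specify two-sample t-tests plus a cluster analysis, and SAP 9.2 removes the cluster analysis.

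**The concern.** Three verdicts side by side invite comparison. If one tertile is significant and another is not, the natural summary is that the device works in one kind of PCI and not in the other. That is a statement about a difference between effects, and the plan produces neither an estimate nor a test of that difference. With roughly a third of the subjects in each tertile, a test can miss a real effect simply because the level is small. A pattern across levels may then reflect low power or unequal level sizes and not any difference in what the device does. The stake is how the subgroup tables are read, not the trial's main conclusion.

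**Working it through.** **Inputs (SAP 8.1.1 and 8.1.2).**
- Control mean: "Estimated mean for the Control group = 152.1" ml.
- DCR mean: "Estimated mean for the DCR group = 129.3 (15% reduction"; difference 152.1 − 129.3 = 22.8 ml.
- SD: "Estimated standard deviation = 73.0"; standardized difference 22.8/73.0 = 0.3123.
- One-sided alpha 0.025, two-sample t-test.
- Evaluable per arm: 162 (primary calculation), 177 (secondary calculation, "Sample sizes of 177 for each group achieves 80% power"), or 197 if no one is lost.

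**The plan's own figure.** The SAP states "Sample sizes of 162 for each group achieves 80% power to reject the null hypothesis of equal means". The noncentral t gives 80.03% power at 162 per arm, so the figure reproduces. Overall power is 83% at 177 per arm and 87% at 197.

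**Power in one tertile.** 177/3 = 59 per arm. The noncentrality is 22.8/(73 × √(2/59)) = 1.696 on 116 degrees of freedom, which gives power p = 0.391.

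**Chance of mixed verdicts when the effect is identical in all three tertiles.** The levels hold different subjects, so the tests are treated as independent:
- P(all three significant) = 0.391³ = 0.060
- P(none significant) = 0.609³ = 0.226
- P(mixed) = 1 − 0.060 − 0.226 = 0.714

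| Evaluable per arm | Power per tertile | P(mixed) |
|---|---|---|
| 162 | 36% | 69% |
| 177 | 39% | 71% |
| 197 | 43% | 73% |

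The within-tertile SD is not given. For assumed values of 50 to 65 ml at the planned difference, P(mixed) is 58% to 75%.

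**Comparison with an interaction test.** In 40,000 simulated trials with a uniform 22.8 ml effect (SD 73, 59 per arm per tertile), the separate tests were mixed in about 72%. A 2-df interaction test at 5% signalled heterogeneity in about 5%. It was non-significant in about 93% of the mixed trials.

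**Dependence on the effect size.** The retrospective pilot in SAP Table 2 has a difference of 152.1 − 118.8 = 33.3 ml, with SDs 73.0 and 49.7. With equal arms these combine to √((73.0² + 49.7²)/2) = 62.4. SD 50 is an assumed lower value.

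| SD (ml) | P(mixed), 59 per arm per tertile | P(mixed), about 66 per arm per tertile |
|---|---|---|
| 73 | 64% | 58% |
| 62.4 | 44% | 36% |
| 50 | 15% | 10% |

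**Vessel levels.** The documents give no split, so these shares are assumptions (planned effect, SD 73, 177 per arm).

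| 1 / 2 / 3+ vessels | Power by level | P(mixed) |
|---|---|---|
| 50/35/15% | 54% / 41% / 20% | 74% |
| 70/25/5% | 69% / 31% / 9% | 78% |
| 90/8/2% | 79% / 12% / 5% | 82% |

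**What an interaction test could detect.** The variance of each tertile difference is 73² × 2/59 = 180.6. For true effects of 11.4, 22.8 and 34.2 ml, the noncentrality is (11.4² + 0 + 11.4²)/180.6 = 1.44, and power of the 2-df F test is about 17%. For 0, 22.8 and 45.6 ml the noncentrality is 5.76 and power is about 56%.

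**The case against.** The strongest reply is that the misuse is predicted, not planned. The objective is to assess contrast volume in each group. Neither document says that differing effects will be claimed when one p-value falls below 2.5% and another does not. The analyses are labelled exploratory throughout, and the reader gets a difference with a 95% CI in every level, so overlapping intervals would temper a hasty reading. All of this stands and limits the weight of the point. It does not remove it: the stated decision in each level is a reject rule, the level-specific intervals meet the objective without that rule, and no interval is planned for the difference between levels.

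A second reply is that the remedy is weak, because an interaction test at this size misses moderate differences. That is also true, so the interaction estimate and its interval should carry the message and the p-value should not be read as proof of uniformity.

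A reader might go further and infer that a uniform effect will usually look subgroup-specific whatever the true effect. The documents do not support that. At the pilot's difference with SD 62.4, mixed verdicts across tertiles are a minority. Nor do they show that the 3-or-more-vessel level will be the smallest. That is plausible, but no split is given.

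**Conclusion.** The point holds as a gap in two exploratory analyses. Six within-level reject rules are specified, and nothing measures whether effects differ between levels. At the planned 15% effect, an identical effect in all tertiles gives disagreeing verdicts about 71% of the time (69% to 73% over 162 to 197 evaluable per arm, SD 73). For assumed vessel splits from 50/35/15% to 90/8/2% the figure is 74% to 82% at 177 per arm. At the pilot's 33.3 ml difference the tertile figure ranges from 64% down to 10%, depending on the SD.

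These results assume independent levels of the stated sizes, a common SD across arms and levels, and an effect uniform in ml. A reader might infer that the trial's main evidence is compromised. It is not: the primary and secondary tests and the sample size are unaffected.

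**What to change.** In SAP 8.11.3.2 and 8.11.3.3:

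1. Keep the descriptive summaries and the level-specific differences with 95% CIs already planned.
2. Delete the reject rule within each level.
3. For each factor, fit one model with treatment, subgroup and treatment-by-subgroup, on the same pre-stated scale (ml or log) as the primary analysis. The scale matters because an effect uniform in percent is not uniform in ml when mean volumes differ between levels.
4. Report the interaction estimates with 95% CIs and the two-sided interaction p-value.
5. State that the test has low power (about 17% for true effects of 11.4, 22.8 and 34.2 ml across tertiles), so a non-significant result does not show a uniform effect.
6. Record the change from protocol 7.8.2 and 7.8.3 in SAP 9.2.

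This needs no new data and no extra subjects. The cost is SAP wording, one documented departure from the protocol's t-tests, and a low-powered test that must be reported with its caveat.

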8.11.3.3 Contrast Volume per Simple, Intermediate, Complex PCI subgroup

The total undiluted iodinated contrast volume (in ml) used per PCI (from first positioning the interventional guiding catheter in stable coronary position till end of PCI procedure) in subgroups of simple, intermediate and complex PCI.

Descriptive summaries of the total undiluted iodinated contrast volume will be presented by treatment group and by complexity in tertiles for the FAP and the PP population and will include the number of subjects with non-missing data (n), mean with 95% confidence interval, standard deviation (SD), median, interquartile range (IQR) and minimum and maximum values.

The endpoint will be evaluated per subgroup using a one-sided two-sample t-test. We will test for assumptions, e.g. normality and equal variances. Normality will be checked using histograms and Q-Q plots. If there are strong indications of non-normality, the data will be (log)transformed, and the back transformed results will be presented. Levene's test for equality of variances will be applied. When the p-value of this test is greater than 0.05, then we assume the variances are equal and we will use the arithmetic mean of the variances in calculating the standard error. When the p-value is less than or equal to 0.05, then we assume the variances are unequal and then we will calculate the standard error from the weighted average of the two variances.

The results of the t-test will be displayed as estimates of the between treatment group difference (with 95% confidence intervals) and the (one-sided) p-value for the between treatment group difference. When the p-value is lower than the significance level of 2.5% (alpha) we will reject the null hypothesis.

All subjects in the FAP population will be included in this analysis. The analysis will be repeated for the PP population.

8.11.3.4 Acute Kidney Injury (AKI) Incidence

The total number and percentage of subjects in which Acute Kidney Injury (AKI) diagnosed after PCI. AKI is defined as an absolute SCr increase >0.3 mg/dl within 48 hours post PCI or a relative SCr increase $>50\%$ within 7 days post PCI, or eGFR decrease $>25\%$ within 48 hours post PCI.

Descriptive summaries of AKI incidence will be presented by treatment group for the FAP and the PP population and will include the number of subjects with non-missing data (n), percentages and 95% exact confidence intervals.

Document ID:	<As applicable, per local requirements>	Document title:		Classification:	For internal use
		Statistical Analysis Plan			
Modified:	11MAY2023			Author:	
Version:	3.0	Template ID:	ClinicalStudyTemplate0025	Approver:	
Status:	Final	Template Version Date:	02MAR2018	Page:	33 of 52

Statistical Analysis Plan

The between treatment group difference in AKI incidence will be tested using a Chi-square test. If a Chi square analysis is not possible (i.e. >20% of the expected cell frequencies less than 5), then a Fisher's exact test will be performed instead. The two-sided p-value of this test will be presented. When the p-value is lower than the significance level of 5% (alpha) we will reject the null hypothesis of equal procedural success in both treatment groups.

All subjects in the FAP population will be included in this analysis. The analysis will be repeated for the PP population.

When considering the incidence of AKI in the patient population of this trial (7.1% incidence, but reported from 3% to 19% [Tsai 2014a]) and taking into account the sample size of 394 patients it is not likely this trial will find a significant difference in AKI incidence in the DCR group compared to the control group.

8.11.3.5 Contrast Usage Variability

The following variability parameters of the total undiluted iodinated contrast volume (in ml) used per PCI (from first positioning the interventional guiding catheter in stable coronary position till end of PCI procedure) will be presented by treatment group for the FAP and the PP population:

- standard deviation
- interquartile Range (IQR)
- quartile coefficient of dispersion $((Q3-Q1)/(Q3+Q1))$, where Q1 and Q3 are the first and third quartiles)
- relative standard deviation (SD divided by the average, also known as coefficient of variation).

We will test for a difference between variances in both groups using the Brown-Forsythe test. The p-value of the test will be presented. When the p-value is lower than the significance level of 5% (alpha) we will reject the null hypothesis of equal variances between groups.

All subjects in the FAP population will be included in this analysis. The analysis will be repeated for the PP population.

8.11.3.6 Fluoroscopy and Procedure Time

The fluoroscopy and procedure time per PCI (from first positioning the interventional guiding catheter in stable coronary position till end of PCI procedure) by treatment group.

Document ID:	<As applicable, per local requirements>	Document title:	Classification:	For internal use
Modified:	11MAY2023	Statistical Analysis Plan	Author:	
Version:	3.0	Template ID: ClinicalStudyTemplate0025	Approver:	
Status:	Final	Template Version Date: 02MAR2018	Page:	34 of 52

Statistical Analysis Plan

Descriptive summaries of the fluoroscopy and procedure time in minutes will be presented by treatment group for the FAP and the PP population and will include the number of subjects with non-missing data (n), mean with 95% confidence interval, standard deviation (SD), median, interquartile range (IQR) and minimum and maximum values. The analysis will be repeated for the PP population.

The endpoints will be evaluated separately using one-sided two-sample t-tests. We will test for assumptions, e.g. normality and equal variances. Normality will be checked using histograms and Q-Q plots. If there are strong indications of non-normality, the data will be (log)transformed, and the back transformed results will be presented. Levene's test for equality of variances will be applied. When the p-value of this test is greater than 0.05, then we assume the variances are equal and we will use the arithmetic mean of the variances in calculating the standard error. When the p-value is less than or equal to 0.05, then we assume the variances are unequal and then we will calculate the standard error from the weighted average of the two variances.

The results of the t-test will be displayed as estimates of the between treatment group difference (with 95% confidence intervals) and the (one-sided) p-value for the between treatment group difference. When the p-value is lower than the significance level of 2.5% (alpha) we will reject the null hypothesis.

All subjects in the FAP population will be included in this analysis. The analysis will be repeated for the PP population.

8.11.3.7 X-ray Dose

The total DAP and AK per PCI (from first positioning the interventional guiding catheter in stable coronary position till end of PCI procedure) by treatment group.

Descriptive summaries of the total DAP (Gy*cm²) and AK (mGy) per PCI will be presented by treatment group for the FAP and will include the number of subjects with non-missing data (n), mean with 95% confidence interval, standard deviation (SD), median, interquartile range (IQR) and minimum and maximum values.

The total DAP and AK will be evaluated separately using one-sided two-sample t-tests. We will test for assumptions, e.g. normality and equal variances. Normality will be checked using histograms and Q-Q plots. If there are strong indications of non-normality, the data will be (log)transformed, and the back transformed results will be presented. Levene's test for equality of variances will be applied. When the p-value of this test is greater than 0.05, then we assume the variances are equal and we will use the arithmetic mean of the variances in

Document ID:	<As applicable, per local requirements>	Document title:		Classification:	For internal use
		Statistical Analysis Plan			
Modified:	11MAY2023			Author:	
Version:	3.0	Template ID:	ClinicalStudyTemplate0025	Approver:	
Status:	Final	Template Version Date:	02MAR2018	Page:	35 of 52

Statistical Analysis Plan

calculating the standard error. When the p-value is less than or equal to 0.05, then we assume the variances are unequal and then we will calculate the standard error from the weighted average of the two variances.

The results of the t-test will be displayed as estimates of the between treatment group difference (with 95% confidence intervals) and the (one-sided) p-value for the between treatment group difference. When the p-value is lower than the significance level of 2.5% (alpha) we will reject the null hypothesis.

All subjects in the FAP population will be included in this analysis. The analysis will be repeated for the PP population.

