7.8.7. Exploratory objective: X-ray Dose**Objective**

- To assess the total X-ray dose (DAP, AK) related to PCI in the Dynamic Coronary Roadmap and control group

Endpoint

- The average total DAP and AK per PCI (from first positioning the interventional guiding catheter in stable coronary position till end of PCI procedure) measured by the Philips X-ray system.

Analysis

The objective will be evaluated using a two-sample equal-variance t-test.

All subjects will be included in this analysis.

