8.2 General Considerations

All results will be summarized by treatment group using the following descriptive statistics: n, mean with 95% confidence intervals, standard deviation (SD), median, interquartile range (IQR), minimum and maximum. Categorical data will be summarised for each treatment group as the number and percentage of subjects in each category (including the category 'missing' if applicable). Generally, percentages will be calculated for missing categories and all percentages will be based on total number of subjects in the population (denoted by N on the summary tables and figures) Statistical analysis will be performed using SAS (SAS® Life Science Analytics Framework 5.1.2) and/or R statistical software (<https://www.r-project.org/>).

All data will be listed for the enrolled population. The data will be sorted by treatment group, subject number and date of assessment (if applicable).

All hypotheses will be tested at a 2.5% level of significance using a one-sided test unless otherwise specified.

For summary statistics, the mean and median will be displayed to one decimal place greater than the original value and the measure of variability (e.g., SD) will be displayed to two decimal places greater than the original value. Minimum and maximum will be reported to the same decimal places as the original value. Percentages will be displayed to 1 decimal place. P-values will be reported to three decimal places; p-values less than 0.001 will be reported as $p<0.001$.

Summary tables will have treatment columns labelled as 'Dynamic Coronary Roadmap' or 'Control'. The main data will also be presented per clinical site.

Document ID:	<As applicable, per local requirements>	Document title:		Classification:	For internal use
		Statistical Analysis Plan			
Modified:	11MAY2023			Author:	
Version:	3.0	Template ID:	ClinicalStudyTemplate0025	Approver:	
Status:	Final	Template Version Date:	02MAR2018	Page:	23 of 52

Statistical Analysis Plan

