8.11.1 Primary Efficacy Analysis

The primary endpoint of the study is the average total undiluted iodinated contrast volume (in ml) used per PCI (from first positioning the interventional guiding catheter in stable coronary position till end of PCI procedure) measured by an automatic contrast injector.

Hypothesis

Dynamic Coronary Roadmap reduces the total iodinated contrast volume used on average per PCI. The null and alternative hypotheses are as follows:

$$H_0: \mu_{\text{Control}} - \mu_{\text{DCR1}} \leq 0$$

$$H_a: \mu_{\text{Control}} - \mu_{\text{DCR1}} > 0$$

Where μ_{Control} is the average total iodinated contrast volume usage per PCI for the Control group, and μ_{DCR1} is the average total iodinated contrast volume usage per PCI for the DCR group.

Document ID:	<As applicable, per local requirements>	Document title:		Classification:	For internal use
		Statistical Analysis Plan			
Modified:	11MAY2023	Template ID:	ClinicalStudyTemplate0025	Author:	
Version:	3.0	Template Version Date:	02MAR2018	Approver:	
Status:	Final			Page:	28 of 52

Statistical Analysis Plan

Analysis

Descriptive summaries of the total undiluted iodinated contrast volume will be presented by treatment group for the FAP and the PP population and will include the number of subjects with non-missing data (n), mean with 95% confidence interval, standard deviation (SD), median, interquartile range (IQR) and minimum and maximum values.

The primary endpoint will be evaluated using a one-sided two-sample t-test. We will test for assumptions, e.g. normality and equal variances. Normality will be checked using histograms and Q-Q plots. If there are strong indications of non-normality, the data will be (log)transformed, and the back transformed results will be presented. Levene's test for equality of variances will be applied. When the p-value of this test is greater than 0.05, then we assume the variances are equal and we will use the arithmetic mean of the variances in calculating the standard error. When the p-value is less than or equal to 0.05, then we assume the variances are unequal and then we will calculate the standard error from the weighted average of the two variances.

All subjects in the full analysis population will be included in this analysis.

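### Fluoroscopy time, procedure time and X-ray dose are tested one-sided with no stated direction; if the direction is a reduction, the p-value rule cannot declare an increase

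*SAP*

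**What the plan says.** SAP 8.11.3.7 (X-ray dose): "The total DAP and AK will be evaluated separately using one-sided two-sample t-tests". SAP 8.11.3.6 (fluoroscopy and procedure time): "The endpoints will be evaluated separately using one-sided two-sample t-tests". Both sections use the same rejection rule, "When the p-value is lower than the significance level of 2.5% (alpha) we will reject the null hypothesis", and both display "estimates of the between treatment group difference (with 95% confidence intervals) and the (one-sided) p-value for the between treatment group difference". Neither writes down a null, an alternative or a direction.

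The sidedness matches the default in SAP 8.2: "All hypotheses will be tested at a 2.5% level of significance using a one-sided test unless otherwise specified". Directional hypotheses appear only for the primary endpoint (8.11.1: "Dynamic Coronary Roadmap reduces the total iodinated contrast volume used on average per PCI") and for the angiogram count (8.11.2).

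The protocol objective for dose is neutral: "To assess the total X-ray dose (DAP, AK) related to PCI in the Dynamic Coronary Roadmap and control group". The objective for the two times (Protocol 7.8.6) is framed the same way. The protocol's analysis for each is "The objective will be evaluated using a two-sample equal-variance t-test", with no side named.

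In the same SAP, AKI (8.11.3.4), procedural success (8.11.3.8) and in-hospital MACCE (8.11.3.9) are tested two-sided at 5%. SAP 9.2 records the assumption checks on the t-tests, the move to chi-square or Fisher tests, the removal of the cluster analysis, the SYNTAX tertiles and the analysis populations. It does not mention one-sided testing of time or dose.

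**The concern.** A neutral objective asks whether the arms differ in either direction; a one-sided rule answers for one direction only. For time and radiation both directions are of interest. The device lays a roadmap over live fluoroscopy, so a reader will want to know whether any contrast saving came with more fluoroscopy, a longer procedure or more dose. The pilot results quoted in Protocol 4.2 concern contrast volume and cine runs. They give no figure for time or dose that would justify looking one way. Protocol 14 also gives a relevant lengthening of a procedure as an example within its definition of serious deterioration in health.

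At stake is how these exploratory results are read. If the intended direction is a reduction, a real increase would come out as a failure to reject with a large p-value, and the SAP attaches no reporting rule to that outcome. Because the direction is not written down, the test is also incompletely specified.

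**Working it through.** **1. The plan's own figure.** The documents give no sample size or power for time or dose, so the check is on the primary endpoint (SAP 8.1.1): means 152.1 and 129.3, SD 73.0, one-sided alpha 0.025, power 80%.
- Standardised difference: (152.1 − 129.3)/73.0 = 0.3123.
- Normal approximation: n = 2(1.960 + 0.842)²/0.3123² ≈ 161 per arm.
- Noncentral t: the smallest n reaching 80% is 162 (power 0.800). The stated 162 is reproduced.
- Dropout: 162/0.9 = 180; for the secondary endpoint 177/0.9 = 196.7, rounded up to 197, hence 394 in total.

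The steps below use 177 evaluable per arm.

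**2. What the one-sided rule can do.** Suppose the alternative is a lower mean with the device. An observed increase puts the t statistic on the null side of zero, so the one-sided p exceeds 0.5 and cannot fall below 0.025. Under a true increase of 0.2 SD the rule rejects with probability about 0.00006, and such a rejection would be a false reduction.

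**3. What the planned interval would show.** With 2 × 177 − 2 = 352 degrees of freedom the two-sided 5% critical value is 1.967. In SD units the half-width of the 95% interval is 1.967 × √(2/177) = 0.209. If the interval is two-sided, it lies wholly on the increase side once the observed increase exceeds about 0.21 SD. That is exactly when a two-sided 5% test would reject in that direction.

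**4. Chance of rejecting towards an increase, two-sided 5% test.** The documents give no SD for time or dose, so the true increases are assumptions in SD units.

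| True increase (SD) | 177 per arm | 197 per arm |
|---|---|---|
| 0.1 | 15% | 17% |
| 0.2 | 47% | 51% |
| 0.3123 | 83% | 87% |
| 0.5 | >99% | >99% |

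The same in percentage terms, with an assumed 15% rise in mean dose and assumed coefficients of variation (CV): d = 0.15/CV, noncentrality = d × √(177/2) = 9.407d.

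| CV | d | Noncentrality | Two-sided 5%, towards an increase | One-sided rule for a reduction, any rejection |
|---|---|---|---|---|
| 0.5 | 0.300 | 2.82 | 0.80 | about 0.000001 |
| 0.6 | 0.250 | 2.35 | 0.65 | about 0.00001 |
| 0.8 | 0.1875 | 1.76 | 0.42 | about 0.0001 |

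**5. Cost for a reduction.** One-sided 2.5% and two-sided 5% use the same critical value in the direction of a reduction. The normal-approximation sample size is 161 per arm for both.

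**The case against.** The strongest reply is that the plan already shows an increase. Both sections require the between-arm difference with a 95% interval. Read as the usual two-sided interval, it excludes zero on the increase side with the same probabilities as the two-sided test in step 4. SAP 8.10 also summarises procedure time, fluoroscopy time, Air Kerma and DAP by arm. This stands: what is missing is a declared rule, not the information.

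The one-sided tests also follow a default declared in SAP 8.2, and the two-sided tests for AKI, procedural success and MACCE are permitted exceptions to it. So there is no contradiction inside the SAP. That stands too, although it does not explain why outcomes with neutral objectives were treated differently. The outcomes are exploratory, and SAP 8.15 makes no multiplicity adjustment.

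Three stronger readings are tempting and not supported:
- **That the SAP tests these outcomes for a reduction.** No direction is stated; this is an inference from the primary hypothesis.
- **That the trial could not detect a radiation or time cost.** This is true only of the p-value rule, and only if the direction is a reduction. The interval and the by-arm summaries remain.
- **That the device is expected to raise dose.** The documents do not say so. The mechanism in Protocol 4.2, fewer repeat cine runs, points towards less exposure, and the net direction is left open.

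Nor does the SAP say that a failure to reject will be reported as no difference.

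**Conclusion.** The point holds in a limited form. SAP 8.11.3.6 and 8.11.3.7 set one-sided 2.5% tests with no hypothesis or direction against neutral protocol objectives, and 9.2 does not record the choice. If the direction is a reduction, the formal rule cannot declare an increase of any size. A two-sided 95% interval would show one above about 0.21 SD at 177 per arm.

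The probabilities of 0.80, 0.65 and 0.42 are illustrations. They rest on an assumed 15% rise, assumed CVs and untransformed data; both sections allow a log transformation, under which d = 0.15/CV would not apply directly. The main point needs none of these assumptions.

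Severity is minor. The effect is on the interpretation of exploratory outcomes, and no primary or secondary conclusion changes.

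**What to change.** In SAP 8.11.3.6 and 8.11.3.7:
- state the null hypothesis of no difference between arms for each of the four outcomes;
- replace the one-sided 2.5% tests with two-sided tests at 5%, as already done for AKI, procedural success and MACCE;
- state that the 95% interval for the difference is two-sided, and that an increase with the device will be reported as an increase.

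In SAP 9.2, record the sidedness of these tests, since the protocol gives none.

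The cost is a few sentences. The sample size, and the power to show a reduction, do not change.
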